#### 9.2.3.3.2. Other Variables for SCRI

Due to the self-controlled nature of the SCRI design, time-invariant covariates will not be confounding variables. Regarding potential time-varying confounding variables, increasing age is not expected to significantly change one's risk of GBS over the course of a few months. Thus, no covariates will be used for confounding control.

#### 9.2.4. Data Sources for Research Question 2

This study will be conducted using health plan administrative claims data held by up to 3 national health plans (e.g., Carelon Research, Humana, and CVS Health). These RPs participate in the US FDA's Sentinel System. Additional RPs may be included and will be specified in the SAP. In addition to providing claims data in the SCDM, the RPs will provide scientific input and feedback to support this study. For Research Question 2, the most recently available data refreshed for the Sentinel System will be leveraged if possible, or the RPs will provide a study-specific refresh, as needed.

#### 9.2.5. Study Size for Research Question 2

## 9.2.5.1. Study Size for RCA

## 9.2.5.1.1. Study Size for Historical Comparator RCA

The conditional PmaxSPRT will be used for the historical comparator RCA and requires specification of the number of GBS cases that have accrued in the historical comparator group, which, at this point, is unknown. Assuming between 10 and 20 GBS cases in the historical comparator group (for 10 GBS cases to be observed, approximately 8.8 million comparator vaccinations will need to be included in the RCA; for 20 GBS cases to be observed, approximately 17.5 million comparator vaccinations will need to be included in the RCA), Table 4 contains sample size calculations for the conditional PmaxSPRT analysis when a Wald-type alpha spending plan is specified and a continuous monitoring scheme. Note: the built-in sample size functionality is only available for a continuous monitoring scheme. The statistical signaling criteria might be higher than what is observed in the actual study, where data are expected to arrive in irregular increments over the 3 interim studies.

Assuming 10 events in the historical comparator group and targeting an attributable risk of 10 excess cases per million doses (corresponding to a relative risk of 9.7), 3 GBS cases will need to be observed in the ABRYSVO-exposed group to have 80% power (alpha = 0.05, 1-sided) to reject the null hypothesis of no association. Under the assumption that each ABRYSVO vaccine contributes 21 days of follow-up time, 2.6 million ABRYSVO vaccinees are needed.

Table 4. Sample size calculations for the conditional PmaxSPRT with a Wald-style alpha spending function, no minimum events required to signal

Target attributable risk in excess cases per million doses	Equivalent relative risk	Target power	Type 1 error	GBS cases needed in the ABRYSVO- exposed group a	Assumed number of GBS cases in the historical comparator group b	ABRYSVO vaccinees needed in millions b
2	2.7	0.8	0.05	75	10	65.2
3	3.6	0.8	0.05	15	10	13.0
4	4.5	0.8	0.05	9	10	7.8
5	5.4	0.8	0.05	6	10	5.2
8	8.0	0.8	0.05	4	10	3.5
10	9.7	0.8	0.05	3	10	2.6
2	2.7	0.8	0.05	27	15	23.5
3	3.6	0.8	0.05	11	15	9.6
4	4.5	0.8	0.05	8	15	7.0
5	5.4	0.8	0.05	6	15	5.2
8	8.0	0.8	0.05	4	15	3.5
10	9.7	0.8	0.05	3	15	2.6
2	2.7	0.8	0.05	21	20	18.3
3	3.6	0.8	0.05	10	20	8.7
4	4.5	0.8	0.05	7	20	6.1

5	5.4	0.8	0.05	5	20	4.3
8	8.0	0.8	0.05	4	20	3.5
10	9.7	0.8	0.05	3	20	2.6

a. GBS cases needed was calculated using the R sequential package.

## 9.2.5.1.2. Study Size for Concurrent Comparator RCA

For the concurrent comparator RCA, a binomial variant of the maxSPRT will be used. Sample size calculations were performed (Table 5), again with a Wald-type alpha spending plan and a continuous monitoring scheme.

Targeting an attributable risk of 10 excess cases per million doses (corresponding to a relative risk of 9.7), 8 GBS cases will need to be observed to have 80% power (alpha = 0.05, 1-sided) to reject the null hypothesis of no association. Under the assumption that each ABRYSVO vaccine contributes 63 days of follow-up time, 2.3 million ABRYSVO vaccinees are needed.

Table 5. Sample size calculations for the binomial maxSPRT with a Wald-style alpha spending function, assuming data are evenly spaced over 3 interim tests

Target attributable risk in excess cases per million doses	Equivalent relative risk	Target power	Type 1 error	Total GBS cases neededa	Risk window length, control window length (days)	ABRYSVO vaccinees needed in millionsb
2	2.7	0.8	0.05	31	21, 42	9.0
3	3.6	0.8	0.05	19	21, 42	5.5
4	4.5	0.8	0.05	16	21, 42	4.6
5	5.4	0.8	0.05	12	21, 42	3.5
8	8.0	0.8	0.05	9	21,42	2.6
10	9.7	0.8	0.05	8	21,42	2.3

a. GBS cases needed was calculated using the R sequential package.

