#### 9.2.3.3.1. Other Variables for RCA

Covariates used for confounding control will be detailed in the SAP and may include age at vaccination, sex, an indicator variable for in and out of season vaccinations, an indicator variable for concomitant vaccinations, and a comorbidity score.

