#### 9.2.7.1.3. Sequential Statistical Analysis for Concurrent Comparator RCA

Because the historical comparator group could be subject to secular trends in GBS, a concurrent comparator RCA will also be performed among ABRYSVO-vaccinated individuals. Using a pre-defined risk and control interval following ABRYSVO vaccination, and a time-based stratification approach, the risk of GBS will be evaluated based on the proportion of vaccinated individuals that are in the risk window at the time of the GBS event. More specifically, for each calendar day, the numerator is calculated as the number of ABRYSVO vaccinees in a specific stratum (e.g., age group, sex, RP) who were in the risk interval on that day, and the denominator is calculated as the number of ABRYSVO vaccinees in the same stratum who were in either the risk or control window on that calendar day. This proportion determines the expected number of GBS events in the risk window

which is compared to the observed number of GBS cases in the risk window on that day. This calculation is performed for all GBS cases. A GBS case is only informative if there are vaccinees in both windows (e.g., positivity assumption). A binomial variant of the maxSPRT will be used to analyze the data. An additional advantage of this approach is that it does not need to restrict to a study population who meets the algorithm for increased risk of RSV-LRTD because these ABRYSVO-vaccinated individuals will be presumed to meet the indication. The stratification for calendar time also eliminates any seasonal variation that may be of concern.

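### The 8 cases said to give 80% power in the concurrent-comparator RCA assume a fixed 21:42 split of cases; under the calendar-day analysis that the protocol specifies, seasonal uptake generally raises the number needed

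*Protocol*

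**What the plan says.** Protocol section 9.2.5.1.2 sizes the concurrent-comparator RCA. For 10 excess cases per million doses (relative risk 9.7) it says "8 GBS cases will need to be observed to have 80% power (alpha = 0.05, 1-sided) to reject the null hypothesis of no association". Table 5 gives this as a total case count, with window lengths of 21 and 42 days as the only design input on timing. The case count is then converted to people: "Under the assumption that each ABRYSVO vaccine contributes 63 days of follow-up time, 2.3 million ABRYSVO vaccinees are needed". The abstract (section 4, study size for Research Question 2) repeats both figures.

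Section 9.2.7.1.3 fixes the analysis. Within strata such as age group, sex and research partner, the protocol counts for each calendar day the vaccinees in the risk window and divides by those in either window. That proportion sets the expected number of risk-window cases. The section adds: "A GBS case is only informative if there are vaccinees in both windows (e.g., positivity assumption".

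On timing of vaccination, section 9.2.1 runs the surveillance over 4 RSV seasons, and section 9.2.3.3.1 lists among possible covariates "an indicator variable for in and out of season vaccinations". No section gives an expected uptake curve.

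**The concern.** The protocol sizes one test and specifies another. With a fixed 1/3, every case carries the same evidence. With a calendar-day share, the evidence depends on when in the season the case falls. Early in a season nearly all vaccinees are in the risk window, so the null probability is close to 1 and a risk-window case says little. After the season only the control window is occupied. At relative risk 9.7 most cases fall in the risk window, so the dilution early in the season matters most.

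The stated 80% is therefore not a property of the specified analysis unless uptake is close to even. Section 9.2.1 makes adding research partners or extending surveillance depend partly on reaching a pre-specified number of GBS cases, to be set in the SAP. If that number were taken from Table 5 it could be too low.

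**Working it through.** **Inputs.** From sections 9.2.5.1.2 and 9.2.5.2 and Table 5: background rate 2 per 100,000 person-years, windows of 21 and 42 days, one-sided alpha 0.05, power 80%, 10 excess cases per million doses. The uptake curves below are assumptions.

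**Reproducing the plan.**
- Background cases in 21 days: 2e-5 × 21/365 = 1.15 per million doses. Relative risk: 1 + 10/1.15 = 9.7. Matches.
- Null probability p0 = 21/63 = 1/3. Alternative p1 = 9.7 × p0/(9.7 × p0 + 1 − p0) = 0.829.
- A binomial maxSPRT with 3 equal looks at p0 = 1/3 needs 8 cases (alpha 0.049, power 87.9%). It also returns 31, 19 and 12 for relative risks 2.7, 3.6 and 5.4, as in Table 5. So the table rests on the fixed 1/3.
- A single exact test with 8 cases rejects at 6 or more: alpha 0.020, power 85.7%.
- Vaccinees: 8/(3 × 1.15) = 2.32 million. Matches.

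Separately, the text says "again with a Wald-type alpha spending plan and a continuous monitoring scheme" while the table title says "assuming data are evenly spaced over 3 interim tests". The 8 fits the title; continuous testing gives 77% at 8 cases and needs 9.

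**The specified analysis.** Let R and C be the vaccinees in days 1–21 and 43–84 on a calendar day. The null share is p = R/(R + C), and under the alternative q = 9.7p/(9.7p + 1 − p). Cases were drawn in proportion to 9.7R + C over three yearly seasons, those with p equal to 0 or 1 were dropped, and the number of risk-window cases was tested against its exact null distribution (a sum of unequal Bernoulli variables). To see the dilution: at p = 1/3 a risk-window case has likelihood ratio 0.829/0.333 = 2.49. At an illustrative p = 0.9, q = 8.73/8.83 = 0.989 and the ratio is only 0.989/0.9 = 1.10.

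**Power with 8 total cases, relative risk 9.7.**

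| Assumed uptake | One exact test | Same, 10% of doses out of season | 3-look maxSPRT | Cases for 80% (one exact test, none out of season) |
|---|---|---|---|---|
| Even all year | 86% | – | 82% | 8 |
| Smooth, SD 60 days | 77–78% | 80–81% | 73% | 9 |
| Smooth, SD 45 days | 72% | 75% | 67% | 10 |
| 6-month block | 72% | 78% | – | 10 |
| Smooth, SD 30 days | 53% | 61% | 52% | 14 |
| 4-month block | 61% | 68% | 58% | 12 |
| 3-month block | 47% | 58% | 46% | 15–16 |
| 2-month block | 17% | 33% | – | 20–26 |

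Monte Carlo error and the handling of the curves' tails move entries by up to about 3 points (SD 45 days came out at 69% in one implementation). In the 6-, 4-, 3- and 2-month blocks without out-of-season doses, about 82%, 72%, 63% and 45% of cases fall on days with both windows occupied.

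**Power at the stated number of vaccinees.** At relative risk 9.7, 2.3 million vaccinees yield 2.3 × 1.15 × (9.7 + 2) = 31 cases. With a Poisson case count of mean 31, power is above 99% for 6- and 4-month blocks, about 98% for 3 months and about 86% for 2 months.

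**The case against.** The strongest reply is that the protocol also gives a vaccinee requirement, and that this one is ample. That stands for relative risk 9.7: the 2.3 million is computed at the background rate alone, and the effect itself would produce about 31 cases. A reader might infer that the concurrent RCA is underpowered at its stated size; for that effect the figures do not support this. The cushion is thinner at small effects. At relative risk 2.7, 9.0 million vaccinees yield 9.0 × 1.15 × 4.7 = about 49 cases, with power about 80%, 72% and 47% for 4-, 3- and 2-month blocks.

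A reader might also infer that 8 cases without a signal would be taken as evidence of safety. The protocol contains no such rule. The RCAs are cumulative from October 2024 (section 9.2.1.1), the case number that bears on extending surveillance is left to the SAP, and the self-controlled study follows after 4 seasons even without a signal.

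The 8 might be read as informative cases only. Table 5 says total cases, and the other reading helps only in part. Eight informative cases give about 84%, 80–82% and 76% in 6-, 4- and 3-month blocks, but only about 71% in a smooth season with SD 45 days, where few cases are lost and dilution does the damage. With 3 looks the range over the seasonal curves is 53–75%.

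Finally, the size of the loss depends on curves that the documents do not give, and the covariate list in section 9.2.3.3.1 shows only that out-of-season doses are expected. This is right: the direction is firm, the size is not. The mildest curves tried (SD 60 days with 10% out of season, or a 6-month block with 20%) sit at about 80%.

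**Conclusion.** The concern holds for the cases-needed statement. Eight total cases at relative risk 9.7 give about 86% power when every case has null probability 1/3 or uptake is even. Under the calendar-day analysis they give about 72–81% in mild seasons (a 6-month block, or smooth with SD 45–60 days, with 0–10% of doses out of season) and about 47–68% in 3- to 4-month blocks. Reaching 80% takes about 9–10 cases in the mild smooth seasons and about 12–16 in those blocks. These figures rest on assumed uptake and on one stratum; finer strata by age, sex and research partner were not modelled and could leave more cases uninformative. The plan's arithmetic is correct for the model it uses, and that model is not the specified test. Power at 2.3 million vaccinees for relative risk 9.7 is not in question, nor is the use of 63 days of follow-up to convert cases to vaccinees.

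**What to change.** - Recompute the cases-needed column of Table 5, the text of section 9.2.5.1.2 and the abstract by simulating the analysis in section 9.2.7.1.3 under a stated range of seasonal uptake curves, with uninformative cases dropped.
- State either the power that 8 cases give or the number needed for 80%, and say whether the count means total or informative cases.
- Do not take the pre-specified case number of section 9.2.1 from the current table.
- At each look, report the number of informative cases and their null probabilities beside the total.
- Keep the 63-day conversion, and note that the vaccinee column is computed at the background rate.

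The cost is a short simulation and revised figures in three places. The stated case requirement will probably rise. Data collection and the analysis itself do not change.

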## 9.2.5.2. Study Size for SCRI

A total number of 7 GBS cases in the combined risk and control intervals provides 80% power (alpha = 0.05, 1-sided) to reject the null hypothesis of no association between ABRYSVO vaccination and GBS when the true attributable risk in excess cases per million doses is 10 (which corresponds to a relative risk of 9.7; Table 6). Assuming a conservative background rate of 2 cases of GBS per 100,000 person-years, 7 GBS cases will be observed amongst 2.0 million ABRYSVO vaccinees. The number of ABRYSVO vaccinations needed for this SCRI study may be revised upon a better understanding of the incidence of GBS in individuals 18-59 years at increased risk of RSV-LRTD from Research Question 1.

b. Assuming a conservative background rate of 2 cases of GBS per 100,000 person-years in individuals 18-

 years at increased risk of RSV-LRTD and that each vaccinee contributes 21 days of follow-up.

b. Assuming a conservative background rate of 2 cases of GBS per 100,000 person-years in individuals 18-

 years at increased risk of RSV-LRTD and that each vaccinee contributes 63 days of follow-up.

Table 6. Sample size calculations for the SCRI of
---

Target attributable risk in excess cases per million doses	Equivalent relative risk	Target power	Type 1 error	Total GBS cases needed a	Risk window length, control window length (days)	ABRYSVO vaccinees needed in millions b
2	2.7	0.8	0.05	29	21, 42	8.4
3	3.6	0.8	0.05	16	21, 42	4.6
4	4.5	0.8	0.05	15	21, 42	4.3
5	5.4	0.8	0.05	11	21, 42	3.2
8	8.0	0.8	0.05	8	21,42	2.3
10	9.7	0.8	0.05	7	21,42	2.0

a. GBS cases needed was calculated using the R sequential package.

## 9.2.6. Data Management for Research Questions 1 and 2

Data management for both Research Questions 1 and 2 are detailed in this section.

HPHCI, located in Boston, Massachusetts, will serve as the coordinating center for all activities and objectives in the study. For all objectives except perhaps the medical record review objective in Research Question 1, HPHCI staff or contractors will be responsible for writing and distributing SAS-based programs to participating RPs. The distributed network developed for the Sentinel System will be leveraged wherever possible. In all aspects of the project, RPs will maintain physical and operational control of their data while allowing use of the data to meet the study needs. HPHCI will maintain a secure, distributed, querying webbased portal to enable secure distribution of analytic queries, data transfer, and document storage.

The national health plans that will participate in the study, as well as some of the IDS partners, will have data in the SCDM. One of the IDS partners participating in the medical record review objective may not have their data in the SCDM.

[figure not shown]
The RPs will establish and maintain the administrative, hardware, and software capabilities and capacity to respond to data requests in a timely manner. RPs will also provide data science support with epidemiologic review.

The general analytic workflow is depicted in Figure 3, below. For all objectives except the medical record review in Research Question 1, HPHCI will submit a computer program designed to meet the needs of the study to each participating RP via a secure portal. Next, the participating RPs will receive and run the computer program behind their firewalls, using data formatted to the SCDM. Then, the RPs will review the analysis results and return them to the study coordinating center through a secure portal. The study coordinating center will review and aggregate the results across the RPs. As a final step, the aggregated results will then be transferred to the study team, including the study sponsor.

b. Assuming a conservative background rate of 2 cases of GBS per 100,000 person-years in individuals 18-

 years at increased risk of RSV-LRTD and that each vaccinee contributes 63 days of follow-up.

Figure 3. General analytic workflow

If the medical record review objective in Research Question 1 does not use the distributed approach, a "common protocol" approach will be taken where HPHCI provides the RP(s) with detailed specifications to identify the cohort of interest and generate the aggregated data necessary for analysis.

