#### Study size (Research Question 2)

- Historical Comparator RCA Assuming 10 events in the historical comparator group and targeting an attributable risk of 10 excess cases per million doses (corresponding to a relative risk of 9.7), 3 GBS cases will need to be observed in the ABRYSVO-exposed group to have 80% power (alpha = 0.05, 1-sided) to reject the null hypothesis of no association in a conditional Poisson maximized sequential probability ratio testing (PmaxSPRT) analysis with a Wald-type alpha spending plan and a continuous monitoring scheme. Under the assumption that each ABRYSVO vaccine contributes 21 days of follow-up time, 2.6 million ABRYSVO vaccinees are needed.
- Concurrent comparator RCA Targeting an attributable risk of 10 excess cases per million doses (corresponding to a relative risk of 9.7), 8 GBS cases will need to be observed to have 80% power (alpha = 0.05, 1-sided) to reject the null hypothesis of no association. Under the assumption that each ABRYSVO vaccine contributes 63 days of follow-up time, 2.3 million ABRYSVO vaccinees are needed.

• *SCRI design study* – A total number of 7 GBS cases in the combined risk and control intervals provides 80% power (alpha = 0.05, 1-sided) to reject the null hypothesis of no association between ABRYSVO vaccination and GBS when the true attributable risk in excess cases per million doses is 10 (which corresponds to a relative risk of 9.7). Assuming a conservative background rate of 2 cases of GBS per 100,000 person-years, 7 GBS cases will need to be observed amongst 2.0 million ABRYSVO vaccinees.

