# 9.2.1.2. Study Design for SCRI

There are 2 scenarios in which the SCRI study may be initiated: 1) if a statistically significant positive association between risk of GBS and ABRYSVO vaccination arises from any RCA, or 2) after 4 RCA seasons, if there was no risk detected. In the former scenario, the SCRI study will serve as refinement of the RCA finding, given the improved control of confounding with the SCRI design, to determine whether a true association exists.

The SCRI design is ideal for studying acute events (e.g., GBS) with well-defined risk periods after a transient exposure.  The incidence of events within a risk window is compared to the incidence of events within a control window. A strength of this design is its ability to control for time-invariant confounders, such as race and age. Time-varying confounders such as seasonality are not controlled unless explicitly accounted for in analyses.

The study population (detailed in Section 9.2.2.2) will be comprised of non-pregnant adults 18-59 years who received an ABYRSVO vaccination from 22 October 2024 (the date of FDA approval of ABRYSVO for adults 18-59 years at increased risk of RSV-LRTD) through the most recent data available at the time of the study commencement, which could include multiple RSV seasons.

The SCRI will compare incidence of GBS during a primary risk window of 1-42 days after ABRYSVO vaccination (day 0 is vaccination) with incidence of GBS during the primary control window 43-84 days after ABRYSVO. The 42-day risk window after vaccine administration for GBS is based upon recent studies that have found days 1-42 post-vaccination to contain the time of increased risk. A secondary risk window of 1-21 days and secondary control window of 43-84 days will also be studied in a sensitivity analysis.

GBS will be identified from claims in all eligible individuals using the algorithm specified in Table 1 during risk and control windows. If the SCRI study is triggered due to a statistically significant finding in the RCA, the GBS cases identified in claims will be confirmed via medical record review as part of the signal refinement process. If the SCRI study commences after 4 seasons without a signal in an RCA, the SCRI study will employ PPV-adjustment of the claims-identified GBS cases.

#### 9.2.2. Setting for Research Question 2

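### The SCRI study size in Table 6 is calculated for the secondary 21-day risk window; for the primary 42-day window, a fixed total of 7 cases gives about 30% power, not 80%

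*Protocol*

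**What the plan says.** Section 9.2.1.2 of the protocol defines the primary comparison: "The SCRI will compare incidence of GBS during a primary risk window of 1-42 days after ABRYSVO vaccination (day 0 is vaccination"), set against a control window of days 43-84. The SCRI bullet in the abstract (section 4, study design for Research Question 2) says the same. Days 1-21 appear only as a sensitivity or secondary analysis (sections 9.2.1.2 and 9.2.7.2.3).

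The study size is in section 9.2.5.2. It states: "A total number of 7 GBS cases in the combined risk and control intervals provides 80% power (alpha = 0.05, 1-sided"). This is said to hold "when the true attributable risk in excess cases per million doses is 10 (which corresponds to a relative risk of 9.7; Table 6"), and the section continues: "Assuming a conservative background rate of 2 cases of GBS per 100,000 person-years, 7 GBS cases will be observed amongst 2.0 million ABRYSVO vaccinees". In Table 6 the column headed "Risk window length, control window length (days") reads 21, 42 in every row, and the footnote assumes "years at increased risk of RSV-LRTD and that each vaccinee contributes 63 days of follow-up". The abstract repeats that "A total number of 7 GBS cases in the combined risk and control intervals provides 80% power", again with a relative risk of 9.7 and 2.0 million vaccinees. No SCRI study size for 42/42 windows appears anywhere in the protocol.

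**The concern.** Three inputs depend on the length of the risk window: the relative risk equivalent to a given excess per million doses, the share of cases expected in the risk window under the null, and the person-time per vaccinee. All three are set for 21 days in the study-size section, while the primary analysis uses 42 days. The sentence on 7 cases and 80% power therefore does not describe the primary analysis.

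What is at stake is how readers judge adequacy. The SCRI runs whether or not a rapid cycle analysis signals, so its result may be the study's last word on the risk. Someone checking whether enough cases accrued would measure the observed count against 7. With 42/42 windows, 7 cases can reject the null only if all 7 fall in the risk window.

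**Working it through.** **Inputs, from section 9.2.5.2 and Table 6:** background rate 2 per 100,000 person-years; target attributable risk (AR) 10 excess cases per million doses; one-sided alpha 0.05; target power 80%. Windows: 21/42 from Table 6, 42/42 from section 9.2.1.2. The year is taken as 365.25 days.

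**Formulas.**
- Background per dose: b = 2e-5 × risk days / 365.25.
- Relative risk: RR = 1 + AR / b.
- Share of cases in the risk window: under the null, p0 = risk days / (risk + control days); under the alternative, p1 = RR × risk days / (RR × risk days + control days).
- Test: exact one-sided binomial, conditional on the total number of cases.
- Vaccinees, on the protocol's background-only conversion: cases / (2e-5 × total window days / 365.25).

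**Reproducing the stated figures (21/42).**
- b = 1.15 per million; RR = 1 + 10/1.15 = 9.70; p0 = 1/3; p1 = 0.829.
- With 7 cases the test rejects at 5 or more: actual alpha 0.045, power 89.8%.
- Five cases give 79.5% and six give 72.6%, so 7 is the smallest total that reaches 80%.
- Vaccinees: 7 / (2e-5 × 63/365.25) = 2.03 million.

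Both stated figures are recovered. The other Table 6 rows agree within two cases.

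**Primary windows (42/42), AR 10.**
- b = 2.30 per million; RR = 1 + 10/2.30 = 5.35; p0 = 1/2; p1 = 5.35/6.35 = 0.842.
- With 7 cases, 6 of 7 in the risk window gives p = 0.0625, so only 7 of 7 rejects (p = 0.0078). Power is 0.8425^7 = 30.1%.
- If RR 9.7 is held instead, power is (9.7/10.7)^7 = 50.3%. That corresponds to (9.7 − 1) × 2.30 = 20 excess cases per million, twice the stated target.

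**Cases needed.** Exact power is saw-toothed in the number of cases. At AR 10:

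| Cases | Reject at | Actual alpha | Power |
|---|---|---|---|
| 7 | 7 | 0.008 | 30.1% |
| 12 | 10 | 0.019 | 71.0% |
| 13 | 10 | 0.046 | 86.5% |
| 14 | 11 | 0.029 | 83.3% |
| 15 | 12 | 0.018 | 79.9% |
| 16 | 12 | 0.038 | 90.6% |

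Three rows of Table 6, as stated and as recalculated for 42/42:

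| AR per million | RR, 42 days | Stated cases | Power of stated cases | First total with 80% | 80% at every total from |
|---|---|---|---|---|---|
| 10 | 5.35 | 7 | 30% | 13 | 16 |
| 5 | 3.17 | 11 | 49% | 23 | 26 |
| 2 | 1.87 | 29 | 41% | 69 | 76 |

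**Vaccinees at AR 10, background only, 84 days.** 13 / (2e-5 × 84/365.25) = 2.8 million; 16 / (2e-5 × 84/365.25) = 3.5 million.

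**What 2.0 million vaccinees would deliver if the excess were real.** Expected cases over 84 days are 2.0 million × (2e-5 × 84/365.25 + 10e-6) = 9.2 + 20 = 29.2. Averaging the exact power over a Poisson case count with that mean gives about 98%.

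**The case against.** The strongest reply is that a reader might take the 30% as the power of the planned study, and infer that a null SCRI at that size would offer false reassurance. The documents do not support that. Table 6 converts cases to vaccinees with the background rate alone. At 2.0 million vaccinees, a true excess of 10 per million would produce about 29 cases rather than 7, and power would be about 98%. The 30% holds only for a fixed total of 7 cases. This part of the reply stands.

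It is also true that the number decides nothing. The SCRI starts on a signal or after four seasons, and uses all data then available (section 9.2.1). Table 6 is correct for the windows it names and still serves the secondary analysis. Both points limit the consequence, but neither makes the sentence on 7 cases true of the primary analysis. Section 9.2.5.2 does allow the number of vaccinations to be revised, but for better knowledge of GBS incidence, not for a different window. Nor is this a detail left to the SAP, since the protocol itself states the figures.

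Two further extensions are tempting:
- **The rapid cycle analyses.** Tables 4 and 5 have no 42-day rows, although those analyses are run with both windows. Section 9.2.7.1 names neither window as primary, so this is an omission and not the same contradiction.
- **One-sided sizing beside a reported 95% confidence interval.** The one-sided alpha is stated openly, and the combination is a choice, not an error.

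**Conclusion.** The stated SCRI study size does not match the primary analysis. For 42/42 windows at 10 excess cases per million doses, a fixed total of 7 cases gives about 30% power at one-sided 0.05, or about 50% if RR 9.7 is held; neither is near the stated 80%. The required total is 13 at first attainment and 16 for 80% at every larger total, against 7 stated. The background-only conversion gives about 2.8 or 3.5 million vaccinees, against 2.0 million stated.

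This rests on the protocol's background rate of 2 per 100,000 person-years, on the target being held as an absolute excess per dose (which is how the protocol states it), and on an exact binomial test, which reproduces the protocol's own 7 cases. The finding is an inconsistency in the stated case count and its conversion to vaccinees. It is not evidence that the SCRI at 2.0 million doses is underpowered for an excess of 10 per million.

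**What to change.** Recalculate Table 6, the text of section 9.2.5.2 and the SCRI study-size bullet in the abstract for the primary 42/42 windows, using the protocol's own method. Four entries change: the equivalent relative risk, the cases needed, the vaccinees needed, and the follow-up per vaccinee (84 days in place of 63). Because exact power is saw-toothed, say whether the case count is the first total to reach 80% or the total from which 80% always holds. Keep the 21/42 rows, labelled as the secondary analysis.

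The cost is wording and tables only. Design, data collection and analysis are untouched, but the stated figures become less favourable.
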